### **7.1.8.9 Worsening of Solid Tumor**

Worsening and/or progression of the patient's solid tumor should not be recorded as an AE or SAE. These data will be captured as efficacy assessment data only. If there is any uncertainty about an AE being related only to the disease under study, it should be reported as an AE or SAE.

## **7.2 Expedited Reporting Requirements**

Certain events require immediate reporting to allow the sponsor to take appropriate measures to address potential new risks in a clinical trial. The investigator must report such events (both initial and follow-up) to the sponsor immediately; under no circumstances should reporting take place more than 24 hours after the investigator learns of the event. The following is a list of events that the investigator must report to the sponsor within 24 hours after first learning of the event, regardless of relationship to study drug:

- Serious adverse events (from informed consent to 30 days following the last dose of study drug or a new treatment of anti-tumor therapy)
- Potential DILI events, regardless of seriousness
- Severe hemorrhagic events (NCI CTCAE Grade  $\geq 3$ ), regardless of seriousness
- Pregnancies
- SAEs occurring beyond the above-mentioned time limit (30 days after the discontinuation of the study drug), if considered related to the study investigational drug, should also be reported to the sponsor.

## **7.3 Duration of Follow-Up for Adverse Events**

The investigator will follow all unresolved AEs and SAEs until the events are resolved or stabilized, the patient is lost to follow-up, or it has been determined that the study treatment or participation is not the cause of the AE/SAE. Resolution of AEs and SAEs (with dates) should be documented on the appropriate CRF and in the patient's medical record to facilitate source data verification (SDV). For SAEs, if, after follow-up, return to baseline status or stabilization cannot be established, an explanation should be recorded in the additional case details section of the CRF.

For some SAEs, additional case details deemed necessary to evaluate the SAE report (eg, hospital discharge summary, consultant report, or autopsy report) appropriately may be followed-up by telephone, fax, email, and/or a monitoring visit to obtain.

All pregnancies that occur during the study should be followed until pregnancy outcome.

## 8 STATISTICAL ANALYSIS

All statistical analysis will be performed under the direction of Hutchison MediPharma personnel.

The final analysis of study data will be based on all patient data up to the time when either all patients have discontinued the study or the study has been terminated. Details of the statistical analysis and data reporting will be provided in the Statistical Analysis Plan (SAP) document finalized prior to database lock.

Data will be summarized using descriptive statistics (continuous data) and/or contingency tables (categorical data) for demographic and baseline characteristics, efficacy measurements, safety measurements, and PK measurements. Information regarding compliance with disease assessments and availability of data will be documented. Graphical techniques (eg, waterfall plots, Kaplan-Meier curves) will be used when such methods are appropriate and informative. The baseline value used in each analysis will be the last (most recent) pre-treatment value. Analyses will be based upon the observed data unless methods for handling missing data are specified. Analyses will be performed using SAS® (Version 9.1 or higher).

### 8.1 Analysis Populations

The following analysis populations are defined for the study:

- Safety Analysis Set (SAS): This population includes all patients who have received at least one dose of fruquintinib. Safety data will be evaluated based on this population's outcome. Patients in the SAS will be analyzed by their actual dose initially received. If patients have dose reduction during the study, all data will be summarized/analyzed based on the initial dose of study drug received.
- Pharmacokinetic Analysis Set (PKAS): This population will include all patients who received at least one dose of fruquintinib and have at least 1 PK sample obtained and analyzed.
- Efficacy Analysis Set (EAS): This population includes all patients who have received at least 1 dose of fruquintinib and have at least 1 post-baseline tumor assessment. All efficacy endpoints will be analyzed based on this analysis set.

### 8.2 Analysis of the Conduct of the Study

A patient listing of all treated patients will be generated to describe site, patient number, screening date, first dosing date, duration of study treatment, analysis set in which the patient is included and disposition. In the patient disposition listing, reason for study drug discontinuation will be included. A table will be created to summarize these categories in terms of number and percent for each of the analysis set defined above.

Patient demographics and baseline characteristics, such as age, sex, race/ethnicity, weight, type of malignancy, duration of malignancy, site of metastatic disease, and baseline ECOG performance status, will be listed and summarized. All summaries will be presented overall, by dose level, and by tumor specific cohorts.

Major protocol deviations related to study inclusion or exclusion criteria, conduct of the trial, patient management, or patient assessment will be listed.

Study drug administration data will be listed by dose level, and any dose modifications will be flagged. Descriptive information will be provided regarding number of cycles, total duration of study drug exposure, actual duration of study drug taken, cumulative dose of study drug, dose intensity and relative dose intensity and the number and timing of prescribed dose reductions and interruptions.

### 8.3 Safety Analysis

Safety will be assessed through AEs, laboratory assessments, vital signs, and ECG results. Safety data will be listed and summarized by dose cohort across the 2 phases. All DLT events will be listed by dose cohort for the dose escalation phase only.

Severity of AEs will be graded by the investigator according to NCI CTCAE v4.03. If a CTCAE criterion does not exist, the grade corresponding to the appropriate adjective will be used by the investigator to describe the maximum intensity of the adverse event: Grade 1 (mild), Grade 2 (moderate), Grade 3 (severe), Grade 4 (life threatening), or Grade 5 (fatal) (see Section 7.1.6). All AEs will be coded with Medical Dictionary for Drug Regulatory Activities (MedDRA).

All AEs will be listed. The focus of safety data summarization will be on treatment-emergent adverse events (TEAEs), which are defined as AEs that occur or worsen in the period extending from the first dose of study drug to 30 days after the last dose of study drug in this study.

TEAEs will be summarized as the number of patients and corresponding percentage by MedDRA System Organ Class (SOC) as well as Preferred Term (PT). The incidence of TEAEs, SAEs, adverse events of special interest (AESIs), AEs leading to dose interruption, reduction, or treatment discontinuation will be presented by SOC and PT; by relationship to the investigational product and by toxicity grade for each dose level. Changes in laboratory data will be summarized by severity grade using the NCI CTCAE v4.03. When abnormal laboratory results at the patient level are counted, the worst value during study treatment will be chosen.

### 8.4 Pharmacokinetic Analysis

Data of plasma concentration versus time are analyzed for PK parameters using the non-compartmental model by WinNonlin enterprise version software. The mean value, standard deviation, coefficient of variation (CV%), median value, minimum value, maximum value, geometric mean value and geometric mean CV% will be reported.

Individual and mean plasma fruquintinib concentration versus time data will be tabulated and presented. The individual and mean PK parameters based on the fruquintinib concentration versus time data, will include, but not be limited to total plasma exposure ( $AUC_{0-t}$  and  $AUC_{0-\infty-\infty}$ ), maximum plasma concentration ( $C_{max}$ ), apparent clearance (CL/F), and apparent volume of distribution ( $V_z/F$ ). The terminal half-life ( $t_{1/2}$ ) will also be estimated. The actual times of plasma sample collection will be used for the PK analysis.

The methods for calculating pharmacokinetic parameters of fruquintinib:

- $C_{\max}$ : the maximum observed plasma concentration over the sampling period, taken directly from the data.
- $T_{\max}$ : time to reach  $C_{\max}$ , taken directly from the data.
- The first-order rate constant associated with the negative slope of the terminal portion of the log-linear concentration-time curve. A minimum of three points will be used.
- Area under the plasma concentration versus time curve (AUC) to be determined by the trapezoidal rule (linear up/log down), where  $AUC_{0-t}$  is the AUC from time zero until the last concentration point and  $AUC_{0-\infty-\infty}$  is the  $AUC_{0-t}$  + last concentration point divided by elimination rate constant ( $K_e$ ).
- Half-life ( $t_{1/2}$ ) to be determined according to  $t_{1/2} = 0.693/K_e$  where possible.
- CL/F: apparent systemic clearance to be determined according to  $\text{dose}/AUC_{0-\infty-\infty}$
- $V_z/F$ : apparent volume of distribution, determined according to  $CL/F/K_e$
- Accumulation ratio:  $AUC_{\text{Day14}}/AUC_{\text{Day1}}$  or  $AUC_{\text{Day21}}/AUC_{\text{Day1}}$

Where the concentration data are missing or listed as less than the lower limit of quantification, they will be regarded as zero (0) if occurring before  $C_{\max}$ . After  $C_{\max}$ , zero points will not be included in calculations.

Individual and mean fruquintinib concentrations will be plotted by dose level.

Pharmacokinetic analysis of fruquintinib and its metabolites will be performed using the same technology.

Venous blood samples for determination of concentrations of fruquintinib in plasma will be taken at the times presented in [Appendix D](#). If dose interruption occurs more than 5 days (including 5 days) of PK sampling, the blood taking should be cancelled or at investigator's discretion. The date and time of collection of each sample and the date and time of dose will be recorded.

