
Safety Assessment
	
All patients who have received at least one dose of fruquintinib will be included in the safety analysis set (SAS).
 
All DLTs will be listed by dose cohort in DLT-evaluable patients for the dose escalation phase only.
 
Safety will be evaluated based on the frequency and severity of AEs, change of laboratory test results, changes in vital signs, change in ECG, and change in echocardiogram. Safety data will be listed and summarized by dose cohort, for patients overall, and for patients with mCRC (cohorts' B and C) and mBC (cohorts' D and E) who received fruquintinib at the RP2D.
 
The severity of all AEs will be graded by the investigator according to the NCI CTCAE v4.03. All AEs will be coded using the Medical Dictionary for Drug Regulatory Activities (MedDRA). Treatment-emergent AEs (TEAEs) will be classified by MedDRA System Organ Class (SOC) and specified by Preferred Term (PT). The incidence of TEAEs, SAEs, adverse events of special interest (AESIs), TEAEs leading to dose interruption, dose reduction, or study drug discontinuation will be summarized.
 
For the laboratory assessments, such as hematology, serum biochemistry, urinalysis, and other urine parameters will be programmatically graded according to CTCAE severity grade. Summary tables will be presented to show the number of patients by CTCAE severity grade with

	
corresponding percentages. For parameters for which a CTCAE scale does not exist, the frequency of patients with values below, within, and above the normal ranges will be summarized. Shift tables for selected hematology and serum biochemistry will also be presented showing change in CTCAE severity grade from baseline to worst grade post-baseline.

Pharmacokinetics	
All patients who received at least one dose of fruquintinib and have at least one plasma sample obtained and analyzed will be included in the Pharmacokinetic Analysis Set (PKAS).
 
A non-compartmental model analysis will be performed for plasma concentration data by the central laboratory using WinNonlin (enterprise version). The following summary statistics will be presented for concentration data and PK parameters, where appropriate: mean, standard deviation, coefficient of variation (CV%), median, minimum, maximum, geometric mean, and geometric mean CV%.

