#### 1.3.1 Clinical Pharmacokinetics

The PK of fruquintinib was evaluated in patients with advanced malignant solid tumors treated with a single-dose or multiple-dose regimen (Study 2009-013-00CH1). Following administration, a single oral dose of 1, 2, 4, 5 and 6 mg, fruquintinib showed a very low clearance. The selection of the once daily (QD) dose regimen was justified by the terminal elimination  $t_{1/2}$  of >35 hours. The AUC and  $C_{max}$  generally increased dose-proportionally at the dose levels from 1 mg to 6 mg. Following multiple dosing, fruquintinib exposure reached steady state after QD administration for 14 days. Based on the AUC for the QD dosing interval (24 hours), accumulation of fruquintinib exposure from the first dose to steady state was approximately 3-fold.

The PK of a 4-week continuous dosing regimen of 5 mg QD was compared to a 3-week continuous dosing regimen of 6 mg QD followed by a 1-week break in fruquintinib therapy in patients with solid cancers (Study 2009-013-00CH1). The PK results showed that fruquintinib PK profiles were similar for the 2 dosing regimens on the same dosing days (see [Table 2](#)).

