### 2.1.3 Secondary Objectives

The secondary objectives of the dose escalation phase include the following:

- To evaluate the PK characteristics of multiple-dose fruquintinib and investigate the metabolite profile of fruquintinib in the plasma of patients with solid tumors.
- To evaluate the anticancer activity of fruquintinib in patients with solid tumors according to Response Evaluation Criteria in Solid Tumors (RECIST) Version 1.1.

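### Protocol 8.4 sets a missing PK concentration to zero if it falls before Cmax, with no limit by day, so a lost early sample at steady state lowers the AUC

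*Protocol*

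**What the plan says.** Protocol 8.4 lists how each PK parameter is calculated and then gives one rule for two situations: where "concentration data are missing or listed as less than the lower limit of quantification, they will be regarded as zero (0" if they occur before Cmax. After Cmax, zero points are left out. The rule names no day and does not separate a lost sample from a measured result below the limit.

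Protocol 8 sets the default: "Analyses will be based upon the observed data unless methods for handling missing data are specified". Section 8.4 does specify a method, so for PK its zero rule governs. AUC is "to be determined by the trapezoidal rule (linear up/log down"), and the accumulation ratio is the Day 14 or Day 21 AUC over the Day 1 AUC.

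The PK tables in Appendix D give profiles at pre-dose, 1, 2, 4, 8 and 24 h. Dose escalation and Cohort A are sampled on Days 1, 14 and 21; Cohorts B to E on Days 1 and 14 only. Protocol 1.3.1 reports that "fruquintinib exposure reached steady state after QD administration for 14 days", with a half-life above 35 h and about 3-fold accumulation. PK is a secondary objective in both phases; for escalation, Protocol 2.1.3 reads "To evaluate the PK characteristics of multiple-dose fruquintinib". SAP 1 places PK outside the SAP, so nothing there changes the rule.

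**The concern.** Before the first dose there is no drug in plasma, so zero is right for a missing Day 1 pre-dose sample. By Day 14 every sample, including the pre-dose one, lies well above zero. A sample that is haemolysed, mislabelled or not drawn says nothing about the concentration, yet the rule turns it into a measured absence of drug.

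The steady-state AUC and the accumulation ratio built on it are at stake. A loss on Day 14 or 21 biases both down. A lost post-dose sample on Day 1 is also zeroed if it precedes Cmax; that lowers the Day 1 AUC and pushes the ratio up.

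The rule also does not fit the AUC method in the same section. A zero at 1, 2 or 4 h creates a segment that falls to zero, and the log-down formula cannot be evaluated there. The analyst would have to improvise.

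**Working it through.** **Inputs** (Protocol Table 2, 5 mg 3 weeks on/1 week off, Day 21): Css_max 383 ng/mL, Css_av 295 ng/mL, AUC0-24 7070 ng·h/mL, DF 43.8%, Tmax 3.6 ± 3.8 h, accumulation index 3.0.

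**Table 2 agrees with itself.** 7070/24 = 294.6, against the stated 295.

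**Trough.** DF is not defined, so three readings were tried:
- (Cmax − Cmin)/Cav: 383 − 0.438 × 295 = 253.8 ng/mL
- (Cmax − Cmin)/Cmin: 383/1.438 = 266.3 ng/mL
- (Cmax − Cmin)/Cmax: 383 × 0.562 = 215.2 ng/mL

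None is near zero. The half-life agrees: at 35 h, 0.5^(24/35) = 62% of a concentration remains after one dosing interval.

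**Which samples precede Cmax.** If every Tmax lay between 0 and 4 h with mean 3.6 h, the SD could be at most √(0.4 × 3.6 × n/(n − 1)), which is 1.7 h at n = 2 and smaller for larger n. The reported SD is 3.8 h, so some peaks come later than 4 h. The pre-dose, 1 h, 2 h and sometimes 4 h samples are therefore exposed.

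**Profiles.** Trough 254 at 0 and 24 h, linear rise to the peak, AUC0-24 held at about 7070:
- Tmax 2 h: 254, 318, 383, 352, 298, 254
- Tmax 4 h: 254, 286, 318, 383, 302, 254
- Tmax 8 h: 254, 264, 275, 296, 338, 254 (holding the AUC forces a peak of 338, not 383)

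Rising segments use (C1 + C2)Δt/2. Falling segments use (C1 − C2)Δt/ln(C1/C2). Segments falling to zero are taken as linear, the milder choice, because the log formula tends to zero area there.

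**Worked case: Tmax 4 h, 2-h sample lost.** The full AUC is 270.0 + 302.0 + 701.0 + 1363.6 + 4436.9 = 7073.5. With 2 h set to zero, the 1-2 h segment becomes 143.0 and the 2-4 h segment 383.0, so the AUC is 6596.5, a change of −6.7%.

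| Lost sample | Tmax 2 h | Tmax 4 h | Tmax 8 h |
|---|---|---|---|
| pre-dose | −1.8% | −1.8% | −1.8% |
| 1 h | −4.5% | −4.0% | −3.7% |
| 2 h | see below | −6.7% | −5.8% |
| 4 h | not zeroed | not zeroed | −12.6% |

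**Lost peak.** If the 2-h peak is lost in the Tmax 2 h profile, the largest observed value is 352 at 4 h. The gap then precedes the observed Cmax and is zeroed: 286.0 + 159.0 + 352.0 + 1297.0 + 4406.6 = 6500.6 against 7074.7, or −8.1%. Omitting the point gives (318 + 352)/2 × 3 = 1005.0 for 1-4 h instead of 350.5 + 734.6 = 1085.1, or −1.1%.

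**Sensitivity.**
- A first-order rise (assumed ka 0.3 to 1.5/h, trough 254) gives 1 h −3.9% to −5.1%, 2 h −6.2% to −8.0%, and 4 h −13.2% to −13.6%.
- Troughs of 215 or 266 with a linear rise give pre-dose −1.5% or −1.9%, 1 h −3.3% to −4.6%, 2 h −5.5% to −6.9%, and 4 h −12.5% to −12.7%.
- Omitting a pre-peak post-dose sample changes the AUC by about 0.01% in the linear profiles and by at most 0.6% in the first-order ones.

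These ranges vary one assumption at a time; varying both together widens them a little.

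**Accumulation ratio.** With Day 1 complete and a true ratio of 3.0, a lost pre-dose sample gives 3.0 × (1 − 0.018) = 2.95. A lost 4-h sample gives 3.0 × (1 − 0.126) = 2.62.

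**Cohort mean.** One 6.7% loss moves the mean AUC by 6.7/6 = 1.1% at n = 6, or 6.7/40 = 0.2% at n = 40, other patients being equal.

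**The case against.** The best defence is that little depends on this. The rule acts only when a sample is lost, and no loss rate is given. One loss barely moves a cohort mean. The outputs are secondary and descriptive; the DLT and PFS-rate endpoints are untouched. The synopsis assigns the non-compartmental analysis to the central laboratory, and a PK plan that was not supplied may already handle missing samples properly. All of this stands and limits the severity. It does not repair the protocol text, which such a plan would have to depart from.

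It may also be said that missing was meant as a synonym for below the limit. The sentence lists the two as alternatives; if one meaning was intended, the clarification below is what is needed.

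A reader might infer more than the documents support:
- **False zeros in the concentration tables.** Section 8.4 says "Individual and mean plasma fruquintinib concentration versus time data will be tabulated and presented", and the synopsis says "The following summary statistics will be presented for concentration data and PK parameters", including a geometric mean that a zero would ruin. But the zero rule follows the list of parameter calculations, and its companion sentence speaks of calculations. The synopsis also adds that the statistics are given where appropriate. Reading the rule as covering parameters only is the more natural reading.
- **A ratio always biased down.** A lost post-dose sample on Day 1 raises it, so the net direction is unknown.
- **Day 21 affected in every cohort.** Only dose escalation and Cohort A, about 12 + 6 = 18 of 128 planned patients, have Day 21 profiles.

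**Conclusion.** The rule is wrong as written for steady-state days, and the point is minor. Zeroing one lost sample lowers that patient's AUC0-24 by about 2% (pre-dose), 4-5% (1 h), 6-8% (2 h) or 13% (4 h with a peak at 8 h), and by about 8% if a 2-h peak is itself lost. Simple omission would cost far less.

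The wording of the rule and the implausibility of zero at steady state are firm. The percentages are illustrations. They assume that the Table 2 means, from an earlier study in China, describe these patients; that pre-dose equals the 24-h value; and the profile shapes shown. The 4-h figure is the least secure, because its profile cannot match both the Table 2 peak and the Table 2 AUC. Whether any reported result is altered depends on how many samples are lost and on the PK plan, neither of which can be seen.

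**What to change.** In Protocol 8.4, or in the PK analysis plan recorded as a change from protocol:
- Treat a missing concentration as missing on every day. Omit a missing post-dose point and let the trapezoid span its neighbours.
- Set a value below the quantification limit to zero only on Day 1, before the first quantifiable sample.
- For a missing steady-state pre-dose sample, use the 24-h value of that interval if dosing was uninterrupted; otherwise do not report AUC0-24 for that profile. The condition is needed because section 8.4 addresses sampling only for longer gaps ("If dose interruption occurs more than 5 days (including 5 days) of PK sampling"), and even then leaves it to be cancelled or decided by the investigator. Patients with interrupted dosing may therefore still be sampled.
- State that the zero rule applies to parameter calculation only, so that no missing sample enters the concentration tables as zero.

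The cost is a few sentences. No new samples are needed and no endpoint changes.

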## 8.5 Efficacy Analysis

The efficacy endpoints include PFS, ORR, DCR, and OS. Efficacy data will be listed and summarized by dose cohort and disease type.

The ORR and DCR will be summarized with percentages and 95% exact confidence intervals. The PFS rate at week 12 (Cohorts B and C) and week 16 (Cohorts D and E) and its 95% confidence intervals will be estimated by the Kaplan-Meier method. PFS, DoR, and OS will be summarized descriptively using Kaplan-Meier medians and quartiles. Percentage change in tumor size from baseline will be determined for patients with measurable disease at baseline and derived at each visit by the percentage change in the

sum of the diameters of target lesions (TLs) compared to baseline. Best percentage change in tumor size will be summarized using descriptive statistics and presented using a waterfall plot.

